5.3.6 Treatment of patients with FVIII inhibitors

Approximately 20–30% of PUPs with severe haemophilia A develop inhibitors to infused FVIII rendering use of such replacement therapy ineffective. Patients who develop inhibitory antibodies remain at higher risk for morbidity and mortality associated with recurrent or uncontrolled bleeding events.

The majority of haemophilia patients with inhibitors develop high-titre (> 5 BU) inhibitors, and demonstrate an anamnestic rise in their inhibitor titre when re-exposed to FVIII. In these patients even frequent, high-dose FVIII substitution therapy becomes ineffective in controlling bleeding episodes as the infused coagulation factor products are neutralised by the inhibitor. Administration of FVIII bypassing agents (rFVII or activated prothrombin complex concentrates) becomes necessary for treatment of bleeding episodes.

Treatment of bleeding episodes with by-passing agents, i.e. rFVIIa or APCC according to local standard care, is allowed for patients who develop FVIII inhibitors within this trial. By-passing agents are not considered trial medication.

The ultimate goal of treatment in patients with high-titre inhibitors is to permanently eradicate the inhibitor by immune tolerance induction therapy (ITI), thereby making it possible for the patient to be treated routinely with FVIII replacement therapy. The therapeutic concept is based on long-term uninterrupted high exposure to FVIII in an effort to sufficiently tolerize the immune system. In that state, the clinical responsiveness to FVIII replacement therapy is restored.

Based on the available evidence, all patients with high-titre inhibitors (> 5 BU) should undergo ITI using the same type of product that the patient was using at the time of inhibitor development. This approach is supported by an international expert panel which concurred with treatment guidelines which recommend that ITI should be conducted with the same concentrate as the one against which antibodies were developed. This should ensure successful tolerance induction and reduce the risk of further inhibitor development to new molecules. It may therefore be expected that N8-GP will be favourable over the use of commercially available FVIII products for ITI in patients who developed FVIII inhibitors within this trial.

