8.2.3 Treatment of bleeding episodes in inhibitor patients

Bleeding episodes in inhibitor patients that do not respond sufficiently to N8-GP treatment may be treated with by-passing agents according to local practice.

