8.2.4 Prohibited medication

Treatment with other FVIII concentrates are not allowed during the course of the trial. If possible, use of Tranexamic acid should be avoided.

Heparin sealing of central venous access ports and cannulae is allowed.

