8.4.3 Blood sampling in infants and children

The blood sampling volume for the patient must not exceed 1% of the total blood volume at one occasion or 3% within in 28 days. This is in accordance with European regulatory guidelines (Directive 2001/20/EC)²².

The total volume of blood to be collected for each patient per visit will not exceed 10 mL.

Detailed instructions will be provided to the trial sites regarding blood sampling volumes and prioritisation of the samples. If trial sites as part of routine assessments perform additional blood draws, they must ensure that the blood sampling volume will not exceed the above requirements.

It is recommended not to attempt venepuncture more than 3 times for the purpose of obtaining sufficient blood sampling. Documentation must be available in medical record.

Port-a-caths and other central venous access devices should preferably not be used for blood sampling due to a risk of dilution or contamination with drugs (e.g. heparin). Should it be necessary to use such a device, it should preferably have been locked with saline prior to use.

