5.3.6 Treatment of patients with FVIII inhibitors

Patients who develop FVIII inhibitors during this trial may receive N8-GP and/or Treatment of bleeding episodes with by-passing agents, e.g. i.e. rFVIIa or APCC for treatment of bleeding episodes according to local standard care is allowed for patients who develop FVIII inhibitors within this trial. However, N8-GP dose levels used should not exceed 75 U/kg as a single dose and not exceed 200 U/kg as a maximum 24 hour dose. Treatment with FVIII concentrates other than N8-GP is not allowed. By-passing agents are not considered trial medication.

The ultimate goal of treatment in patients with high-titre inhibitors is to permanently eradicate the inhibitor by immune tolerance induction therapy (ITI), thereby making it possible for the patient to be treated routinely with FVIII replacement therapy again. The therapeutic concept is based on long-term uninterrupted high exposure to FVIII in an effort to sufficiently tolerise the immune system. In that state, the clinical responsiveness to FVIII replacement therapy is restored.

Novo Nordisk plans that Patients who develop inhibitors, within this trial, will be offered continued treatment with N8-GP, including ITI for a maximum of 24 months. ITI with N8-GP will not be initiated until Novo Nordisk has reviewed the clinical data available after completion of the N8-GP pivotal and surgery trial (pathfinderTM2 and pathfinderTM3), and of the paediatric PTP trial (pathfinderTM5) data needed for opening the paediatric PUP trial according to EMA requirements.

It is expected to use a N8-GP dosing regimen for ITI similar to local standard care/guidelines applied for ITI with marketed FVIII products. For each individual patient, ITI regimens with N8-GP would have to be reviewed by the investigator every month, and more formally reviewed every 3 months by Novo Nordisk.

If patients with (usually low titre) inhibitors respond well to treatment with N8-GP then the patient can continue the prophylaxis. These patients can still start ITI treatment within 6 months after the

Protocol Amendment
Trial ID: NN7088-3908

CONFIDENTIAL

Date: 20 March 2015 | Novo Nordisk
Version: 2.0

UTN: U1111-1148-1897 CONFIDENTIAL Status: Final Page: 14 of 41

confirmatory inhibitor test. If the inhibitor is still present (BU>/=0.6) at 6 months after the confirmatory test the patient must start ITI or withdraw from the trial.

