6.4 Withdrawal criteria

The patient must be withdrawn if the following applies:

- 1. Dosed in the trial, but not fulfilling the inclusion and/or exclusion criteria
- 2. Anaphylactic reaction to the trial product, for definition see Section 11.1

Major surgery before 50 EDs, see Section 5.3.4

Significant thromboembolic event, see Section 11.1

Incapacity or unwillingness to follow trial procedures

Use of coagulations factors other than N8-GP or anti-coagulants unless in relation to ITI

ITI treatment has not been started within 6 months from the date of confirmation of positive FVIII inhibitor (BU $\geq 0.6 \frac{\text{ml}}{\text{ml}}$) unless the FVIII inhibitor has disappeared (BU<0.6) under continuous prophylactic treatment within the 6 months.

FVIII inhibitor titre decline from peak level is less than 20% after 12 months of ITI treatment FVIII inhibitor is positive (BU $\geq 0.6 \frac{\text{ml}}{\text{ml}}$) after 24 months of ITI treatment.

After completed ITI treatment (maximum 24 months), prophylaxis treatment as described in the protocol is not resumed/started

Positive inhibitor test result from visit 1 before first dosing (a positive sample does not have to be confirmed in a confirmatory test)

Participation in another clinical trial throughout the trial.

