8.7 Surgery

Before any surgery is performed blood samples for assessment of inhibitors must be taken and send to central lab unless a test has been taken and send to central lab within 30 days (but the results does not have to be available before the surgery).

Preventive N8-GP treatment before minor surgery including placement or removal of central venous access port can be performed *during* within this trial at the investigator's discretion according to local guidelines. A dose of 40-75 U/Kg N8-GP prior to minor surgery is recommended to prevent perioperative bleeding episodes, see Table 5-1. Major surgeries are only allowed after 50 EDs and when the results from the pathfinder^{TM6} (NN7088-3860) is available. *Prior to major surgery a dose of maximum 75 U/kg is recommended*, see Section 5.3.5.

Preventive N8-GP treatment prior to surgery should be captured in eCRF or in the eDiary.

Emergency surgeries are allowed in this trial if adequate supply of N8-GP is available at site to ensure haemostasis and wound healing.

Patients undergoing surgery will continue the regular visit schedule, but additional visits may be performed in the peri-operative period as decided by the investigator. Surgery will be documented as unscheduled visits. It is up to the investigator to decide how long the post-surgery period should be and when the patient should resume regular prophylaxis or pre-prophylaxis treatment. All N8-GP doses administered in relation to a surgery must be registered on the surgery from in the eCRF.

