8.7.1 Data collection during Major surgery

Definition of *minor and* major surgery, see Section 5.3.5

Protocol Amendment	CONFIDENTIAL	Date:	20 March 2015	Novo Nordisk
Trial ID: NN7088-3908		Version:	2.0	
UTN: U1111-1148-1897		Status:	Final	
EudraCT No.: 2013-004025-88		Page:	33 of 41	

FVIII inhibitor sample should be taken prior to surgery and analysed at the central laboratory. For major surgery surgeries the following should be recorded in the eCRF:

- Date, time and volume of preventive dose before surgery
- Type of surgery
- Indication for surgery
- Date of surgery
- Start and stop time of surgery*
- Dosing of N8-GP in relation to the surgery
- Clinical evaluation of haemostatic response, see Table 8-1 8-2
- Concomitant medication incl. blood products
- Adverse events
- Clinical narrative of the procedure
- Withdrawal criteria (e.g. if other than the trial drug is used)

Injections with N8-GP administered after surgery has been completed should be reported either in the eCRF (injections administered at site) or in the eDiary (injections administered at home), see Section 12.3

Clinical evaluation of haemostatic response to be evaluated upon completion of the surgical procedure by the Surgeon, Anaesthesiologist and/or Investigator, based on experience as follows:

Table 8-2 Haemostatic response for Surgery - 4-point scale

Classification	Description
Excellent	Better than expected/predicted in this type of procedure
Good	As expected in this type of procedure
Moderate	Less than optimal for the type of procedure but haemostatic response maintained without change of treatment regimen
None	Bleeding due to inadequate therapeutic response with adequate dosing, change of regimen required

...

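### Withdrawal criterion 6 exempts only use related to ITI, so read literally it conflicts with the sections that permit by-passing agents in inhibitor patients and, less clearly, heparin sealing of ports

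*Combined protocol and SAP*

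**What the plan says.** **The rule.** Section 6.4 has a list of conditions under which the patient must be withdrawn. The sixth is "Use of coagulations factors other than N8-GP or anti-coagulants unless in relation to ITI". The words are the same in protocol version 1.0 and in Amendment 2. No later amendment, as printed, changes them.

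**By-passing agents.** Section 5.3.6 of version 1.0 says that treatment of bleeds with by-passing agents, namely "rFVIIa or APCC according to local standard care, is allowed for patients who develop FVIII inhibitors within this trial". Amendment 2 rewords this paragraph but keeps the permission for patients who develop inhibitors. Section 8.2.3 says that bleeds in inhibitor patients "that do not respond sufficiently to N8-GP treatment may be treated with by-passing agents according to local practice". Neither section makes ITI a condition.

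**Inhibitor patients without ITI.** Section 5.3.6 in Amendment 2 adds: "If patients with (usually low titre) inhibitors respond well to treatment with N8-GP then the patient can continue the prophylaxis". Withdrawal criterion 7, as amended, spares a patient who has not started ITI if the inhibitor has fallen below 0.6 BU on continued prophylaxis within 6 months of confirmation.

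**Heparin.** Section 8.2.4 states: "Heparin sealing of central venous access ports and cannulae is allowed". It sets no condition on inhibitor status or ITI.

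**Signs of intent.** Section 8.9 discusses withdrawal for use of FVIII concentrates other than N8-GP and refers the reader to 8.2.3 for by-passing agents. Section 8.2.2 in Amendment 2 has by-passing agents recorded as concomitant medication.

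**The concern.** A mandatory withdrawal rule should not cover treatment that the same protocol allows. Criterion 6 has one exception, and that exception is narrower than the permissions given elsewhere. The flow chart (Table 2–1) has sites check the withdrawal criteria at every visit from V1 to end of trial, so the text is in regular use.

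A site that applies 6.4 to the letter could withdraw a child for a permitted treatment, while another site that relies on 5.3.6, 8.2.3 or 8.9 would keep an identical child. Withdrawal cannot be undone, because exclusion criterion 3 and section 8.1 bar a dosed patient from returning. It also ends follow-up for bleeding rate, later inhibitor titre and adverse events.

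**Working it through.** The plan gives no figure on this point, so the check is a comparison of texts, followed by a ceiling on how many patients the main conflict could reach.

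**1. Does a by-passing agent fall under criterion 6?** Yes. The abbreviation list defines rFVIIa as activated recombinant factor VII and APCC as activated prothrombin complex concentrate. Both are coagulation factor products other than N8-GP.

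**2. Is the use always related to ITI?** Take inhibitor patients in three groups.

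- *On ITI.* The exception applies and there is no conflict.
- *Awaiting ITI.* Section 8.1.11 in Amendment 2 allows by-passing agents within the section on ITI visits, before it turns to what happens once ITI is initiated. A site could reasonably treat this as use related to ITI. The conflict is arguable only.
- *Never starting ITI, and not withdrawn under criterion 7 because the inhibitor disappeared within 6 months.* There is no ITI for the use to relate to. Sections 5.3.6 and 8.2.3 permit the treatment and criterion 6 requires withdrawal. The conflict is clear.

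**3. How large could the third group be?** Section 5.3.6 expects inhibitors in 20–30% of these patients, and section 6.1 plans 125 started on trial product. Expected inhibitor patients:

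- of 125: 0.20 × 125 = 25 to 0.30 × 125 = 37.5;
- per 50, since Amendment 8 ends recruitment short of plan: 0.20 × 50 = 10 to 0.30 × 50 = 15.

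These are ceilings on all inhibitor patients. The third group given by-passing agents is an unknown subset. It is probably small: those who continue prophylaxis are described as responding well to N8-GP, whereas 8.2.3 directs by-passing agents to bleeds that do not respond sufficiently. It need not be empty, because 5.3.6 permits the agents more broadly than 8.2.3.

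**4. Heparin.** Criterion 6 names anti-coagulants and does not separate sealing a device from treating the patient. A child without an inhibitor has no ITI, so the exception cannot cover him. Ports are foreseeable, since section 8.7 says "minor surgery including placement or removal of central venous access port can be performed" during the trial. The documents give no rate of port use or heparin sealing, so no count or useful ceiling follows.

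**5. Effect on the primary rate.** Under section 16.3 the numerator is patients with inhibitors, and the denominator is all with at least 10 exposure days plus any earlier inhibitor cases. Section 17.2 keeps data collected before withdrawal. A patient with a confirmed inhibitor therefore stays in both, whether or not he is later withdrawn.

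**The case against.** The strongest reply is that the protocol answers the question elsewhere. The permissions are specific and repeated, and 8.9 takes a reader who is thinking about withdrawal directly to the section that allows by-passing agents. A specific permission is normally read as qualifying a general rule. This stands as evidence of intent and is the main reason the point is minor. It does not change the wording of a list headed by a mandatory instruction, and Amendment 2 edited that list without aligning this entry.

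The heparin reading is also open to challenge, and the challenge largely stands. Section 8.2.4 is an express carve-out under the heading on prohibited medication, and sealing a device can be read as not giving the patient an anti-coagulant. A reader might look for support in the surgery data list of Amendment 2, with its entry "Withdrawal criteria (e.g. if other than the trial drug is used", or in section 8.4.3, which discourages sampling from access devices "due to a risk of dilution or contamination with drugs (e.g. heparin". Neither shows a conflict. The first reads naturally as another haemostatic product used in place of N8-GP, and the second is about sample quality.

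A reader might also infer that children would lose in-trial ITI. The documents give little support for this. Patients who never start ITI lose none, and for those heading towards it the existing exception plausibly applies.

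**Conclusion.** The inconsistency is real and minor. It is clear for by-passing agents in inhibitor patients who never start ITI, arguable for those awaiting ITI, and weak for heparin sealing. The consequence is possible inconsistent or wrongful withdrawal, with shortened follow-up, at sites that apply 6.4 literally. This rests on the assumption that some sites would do so despite 8.9.

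The number affected is unknown and probably small; the documents give no rate of by-passing use outside ITI, of ports or of heparin sealing.

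A reader might infer a measurable bias in the inhibitor rate, reasoning that an inhibitor-free child withdrawn for a heparin-sealed port either drops out of the denominator or has his observation cut short. The documents do not support putting a figure on this. It depends on the weaker conflict and on an assumed share of ports. It also needs a denominator that is not fixed in advance: 50 patients with 50 exposure days is the trigger for the main report, but section 16 also includes data from patients who have not yet completed the main phase, so the number with at least 10 exposure days would normally exceed 50. Sites must also aim to hold an end-of-trial visit for withdrawn patients, and that visit includes an inhibitor test.

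**What to change.** Amend criterion 6 in section 6.4 to read: *Use of coagulation factors other than N8-GP, or anti-coagulants, except by-passing agents given to patients with FVIII inhibitors (sections 5.3.6, 8.1.11, 8.2.3), use in relation to ITI, and heparin sealing of venous access ports and cannulae (section 8.2.4).*

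The cost is one amended sentence. It needs no new data, visits or analyses, and no change to section 16.

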6.6.3 Rationale for withdrawal criteria

- Criteria nos. 1-6 are included to protect the patient's safety and reliability of the data.
- Criteria nos. 7-1012 are included to ensure appropriate treatment of inhibitor patients.

Protocol Amendment
Trial ID: NN7088-3908

CONFIDENTIAL

Date: 20 March 2015 | Novo Nordisk
Version: 2.0

7 Milestones

Planned duration of recruitment period (FPFV – LPFV): approximately 42 months

Planned FPFV: 26-Jun-2014 01 May 2014

Planned LPFV: 02 October 2020 02 Apr 2018

End of trial is defined as LPLV: 13 November 2021 13 May 2019

The duration of the trial for each individual country will vary. However, the end of trial will be no later than 13 May 2019 13 November 2021

The end of the clinical trial is defined as last visit of the last patient.

Planned completion of clinical trial report (CTR): November 2019 14 May 2022.

The duration of N8-GP treatment in the trial is a minimum total 100EDs for a particular patient. Once a patient has achieved 100EDs, they may be offered the option to continue in the trial until either N8-GP is commercially available in the relevant country or until the marketing authorisation application for N8-GP is rejected in the relevant country unless the N8-GP trial, part of the trial or a trial site is terminated by Novo Nordisk or a relevant authority for any reason. In any event, the LPLV for the trial will be no later than *13 November 2021* 30 June 2018 whether or not the product is commercially available in the relevant country.

8 Mathods and assessments

. . .

Fig 8-1: added to pre-prophylaxis box – Visits at: ED 5,10,15,20

• • •

Screening and enrolment log

. . . .

At screening, patients will be provided with a trial card stating that they are participating in a trial and giving contact address(es) and telephone number(s) of relevant trial site staff. Patient's parent(s)/LAR(s) should be instructed to return the trial card to the investigator at the last trial visit or to destroy the trial card after the last visit.

Each patient will be assigned a unique 6-digit number. It must be stated in the medical records that the patient is participating in the trial, including the patient number.

Protocol Amendment
Trial ID: NN7088-3908

CONJUDENTIAL

Date: 20 March 2015 | Novo Nordisk
Version: 2.0

Informed consent procedure

. . .

Informed consent for obtaining genotyping must be collected, if applicable. *Genotype consent is not applicable for Israel*.

. . . .

For withdrawn patients

. . .

The end of trial form must be completed, and final drug accountability must be performed even if the patient is not able to come to the trial site. A withdrawal session must be made in the IWRS and case book must be signed in the eCRF.

. . .

In general

Review of eDiary reports, laboratory reports etc. must be documented either on the front page of the documents and/or in the patient's medical record.

If considered relevant a caregiver can take over the responsibilities from the parent(s)/LAR(s) of handling and administrating the trial drug, filling in the eDiary and attending visits at site. The caregiver must be trained equally as the parent(s)/LAR(s) in the relevant responsibilities. Site must follow the local law and local guidelines for decision of which task a caregiver can take responsibility for.

Site must document correspondence with patient's parent(s)/LAR(s) concerning returning or destruction of trial drug, solvent and injection kits that are to expire or has expired.

. . .

8.1.1 Visit 0 – screening visit

The patient's parent(s)/LAR(s) must give signed and dated informed consent prior to any trial related activities. Signing of the informed consent can take place before visit 0, if allowed by local law. All patients will be provided with a copy on the patient information and a copy of the signed and dated Informed Consent Form.

. . . .

Pre-prophylaxis treatment

Pre-prophylaxis is optional and is the period before start of regular prophylaxis. The pre-prophylaxis period ends when the patient has reached 20 EDs or has turned 24 months of age, whatever comes first, and the patient must begin prophylaxis regimen.

During pre-prophylaxis the following dosing regimen applies:

- approximately 60 U/Kg N8-GP within the range of 50-75 U/Kg bw, see Section 5.3
- individualised prophylactic dosing intervals but less frequent than every 7th day(once weekly)
- on-demand treatment of bleeding episodes or minor surgeries

See further Section 5.3.2.

. . .

